**Figure 1. Four Step Screening Process: Summary of Exclusion Criteria by Steps**

For this within-subject placebo-controlled partially-blinded treatment protocol (Fig 2), we will enroll 48 medically stable Veterans with stabilized recovery trajectories after a stroke or a TBI and who have a homogeneous level of moderately impaired cognitive function persisting after standard rehabilitation.

An equal number of Veterans with stroke/TBI (24-stroke; 24-TBI) will be enrolled, but we will over-sample females (Figure 2). For each iTBS group to include an equal number of Veterans with stroke/TBI, Veterans will be randomly assigned by diagnostic groups, to receive Active iTBS or Placebo iTBS. To measure immediate effects (ImE), an equal number of Veterans with stroke/TBI within each iTBS group will be randomly assigned to be tested with the Modified Digit Span (MDS) or AMPS, three times at 30 min intervals. Persisting effects (PE) tests will be administered to all participants at five timepoints including prior to and after Active iTBS or Placebo iTBS and 2-weeks later prior to the 2nd intervention, where all Veterans receive APT paired with their assigned iTBS (Active iTBS + APT or Placebo iTBS + APT). The alternate ImE test is then administered three times at 30 min intervals, followed by re-administration of all PE tests. Two weeks later, all PE tests are administered a 5th time (B4). ImE and PE measures are used to define magnitude and duration of cognitive change. Randomization (SAS Proc Plan) will be managed by one un-blinded researcher who will not provide interventions or conduct testing.

**Figure 2. Study Design (ImE = Immediate Effects Tests; AMPS = AMPS or MDS = Modified Digit Span; PE = Persisting Effects Tests for all participants; Study Day-1: Obtain Covariates and Treatment preparation information; B0 = Pre-Study-Day-2; B1 = Post-Study-Day-2; After 2-Weeks B2 = Pre-Study-Day-3; B3 = Post-Study-Day-3; After 2-Weeks B4 = Study-Day 4)**

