**Study-Day 2 (4 days after Study Day 1)(~8 hours):**

- 1. PE testing battery
- 2. A single session of **Active** iTBS or **Placebo** iTBS
- 3. Randomly assigned ImE test (MDS or AMPS), administered 3-times at 30 min intervals, each interval includes 5 to 15 min of rest).
- 4. PE testing battery
- 5. Suitability ratings 1-3

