**Study-Day 3 (2 weeks after Study Day 2)(~8 hours):**

- 1. PE testing battery
- 2. Single session **Active** iTBS+ APT or **Placebo** iTBS+APT
- 3. Alternate ImE test (MDS or AMPS) three times at 30min intervals
- 4. PE testing battery
- 5. Suitability ratings 1-3

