**Immediate Effects (ImE) Measures.** For TBI and stroke, *magnitude of cognitive gains immediately after a single session of iTBS to the DLPFC are unknown. For healthy controls, however, working memory shows the most consistent and largest effects (g=.938).* Thus, we will measure immediate change in cognitive capacity according to the domain of working memory using the **MDS**, which is based on the WAIS-IV Digit Span as it enables repeated administration and has an extensive research base and a structure that lends itself to adaptation with less theoretical likelihood of alternate form reliability issues. To minimize potential reliability issues, the *study Neuropsychologist created 6 alternate forms that each retain the underlying WAIS-IV Digit Span subtest structure as closely as possible. Each form uses identical instructions, number of practice and test items, and discontinuation and scoring criteria. Each form also includes a unique systematic randomization of digits where number strings follow the same internal structure including minimization of the digits '9' and '5' in a single string (i.e., 'phonetic similarity'), exclusion of repeated digits and '0' for forward/backward trials, consistent placement of repeated digits and '0's as they occur in the original sequencing trials, and introduction of the sequencing trials with a 'no manipulation' item. Further, no more than two sequential digits are used in any trial, and any instances of sequential digits in the original item content are reflected in the adapted trials.* As each alternate MDS form will be administered *three times in 30 min intervals*, we will **minimize practice effects** by doing an initial randomization of the ordering for administration of the alternate forms. Thus, each Veteran

across all interventions will be tested with the alternate forms in identical order. Since we are not actually testing and establishing the validity of each form, it is critical that the test conditions be identical across participants. If the alternate forms are not perfectly equivalent, then this identical order allows us to control for this issue across participants.

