For measuring immediate changes in cognitive function, we will use the aforementioned **AMPS**. For each of the *three administrations, in 30-min intervals*, a unique task will be randomly selected (without replacement) from the set of tasks developed during Step 4 (Fig 1). Thus, the same IADL is never repeated for the same Veteran.

**Persisting Effects (PE) Measures.** This battery includes the same five tests/sub-tests administered during screening (Fig 1, Step-4: AMPS, RBANS, WAIS-IV Digit Span, DKEFS subtests and BRIEF-A). As the BRIEF-A will be re-administered, the study Neuropsychologist will review BRIEF-A scores and, if there are compelling reasons, Veterans with scores suggesting atypical validity will be withdrawn. This battery also includes tests to measure change in mood: Columbia Suicide Severity Rating Scale (C-SSRS) *Beck Anxiety Inventory (BAI)*, and the *Posttraumatic Stress Disorder Checklist (PCL)*. To assess fatigue, we will use the Fatigue Severity Scale (FSS), which is a self-report measure of prior-week fatigue during nine activities and current fatigue. To measure behavioral features of agitation, we will use the *Agitated Behavioral Scale (ABS)*.

Table 2: Instrumentation: Testing Battery					
Immediate Outcome Effects (ImE)	Hrs/Admin	Aims	Variable Types	# Reps	
AMPS	1.5	1 & 2	Continuous (logit)	3	
Modified Digit Span (MDS)	0.2	1 & 2	Proportional (% correct)	3	
Persisting Effects Testing Battery (PE)	Hrs/Admin	Aims	Variable Types	# Reps	
Repeatable Battery for Assessment of Neuropsych Status (RBANS)	1.0	2	Continuous (normed score)	5	
Weschler Adult Intelligence Scale (WAIS-IV) Digit Span			Proportional (% correct)	5	
Delis-Kaplan Executive Functioning System (DKEFS): Color-Word			Continuous (normed score)	5	
Behavior Rating Inventory of Executive Function (BRIEF)			Continuous (normed score)	5	
AMPS	1.5	2	Continuous (logit)	5	
PTSD Checklist (PCL)	0.1	2 & 3	Mean # symptoms/ severity	5	
Columbia Suicide Severity Rating Scale (C-SSRS)	0.1	2 & 3	Raw score (Veteran rating)	5	
Beck Anxiety Inventory (BAI)	0.1	2 & 3	Raw score (Veteran rating)	5	
Agitated Behavior Scale (ABS)	0.1	2 & 3	Raw score (research clinician rating)	5	
Fatigue Severity Scale (FSS): Prior Week Daily Living Score	0.1	2 & 3	Raw score (Veteran rating)	5	
Fatigue Severity Scale (FSS) L VASF Current Fatigue Rating	0.1	2 & 3	Raw score (Veteran rating)	5	

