Average Placebo iTBS + APT MCG using t-tests for continuous data and z-tests for binary data. Using MLM, we will also determine if Active iTBS is related to more MDS or more AMPS gains. The group (Active iTBS or Placebo iTBS) by time interaction parameter will be used to examine if Active iTBS has a differential trend compared to Placebo iTBS. For 2i, we will also use MLM to identify presence of an additive effect of APT by examining Active iTBS + APT trend lines. For both the AMPS and the MDS outcomes, the group (Active iTBS + APT or Placebo iTBS + APT) by time interaction parameter will be used to examine if the Active iTBS + APT has a differential trend compared to Placebo iTBS + APT. For each intervention we will also determine (2ii) presence of persisting effects of Active iTBS and Active iTBS + APT in the short-term, long-term and cumulatively. Using the PE measures specified in Table 1 and t-tests, we will compare each PE measure for Active iTBS with Placebo iTBS and for Active iTBS + APT with Placebo iTBS + APT. Significant results will be reported. For (2iii), we will use one-tailed t-tests to identify presence of practice effects for MDS and AMPS. We will compare MDS and AMPS average peak gains after Placebo iTBS with average peak gains after Active iTBS. If the average Placebo iTBS peak gain is greater than the average Active iTBS peak gain for either MDS or AMPS, then we will repeat analyses above (for 2i and 2ii) using ImE and PE measures after adjusting them for the detected practice effects.

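### For the Modified Digit Span (MDS), the mixed model's only named parameter, group-by-time over three post-stimulation tests, cannot show whether Active iTBS produced a gain

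*Combined protocol and SAP*

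**What the plan says.** Section 5.6 (Data Analysis), Aim 2 (2i), gives the mixed model its task: "Using MLM, we will also determine if Active iTBS is related to more MDS or more AMPS gains". The next sentence names the parameter: "The group (Active iTBS or Placebo iTBS) by time interaction parameter will be used to examine if Active iTBS has a differential trend". For the second session, presence of an additive APT effect is to be judged from trend lines on both outcomes, again through the group "by time interaction parameter will be used to examine if the Active iTBS + APT has a differential trend compared to Placebo iTBS + APT". No group main effect, average contrast or baseline-adjusted contrast is named. The coding of time is not given.

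The schedule in section 5.1 puts the immediate-effects test after the intervention on both days. On Study-Day 2, after the stimulation item, it lists "Randomly assigned ImE test (MDS or AMPS), administered 3-times at 30 min intervals"; on Study-Day 3, after iTBS + APT, "Alternate ImE test (MDS or AMPS) three times at 30min intervals". Veterans within each iTBS group "will be randomly assigned to be tested with the Modified Digit Span (MDS) or AMPS, three times at 30 min intervals" and take the other test at the second session, so each Veteran meets MDS on one day only. Table 2 lists three MDS repetitions. The battery given before each session contains "Fig 1, Step-4: AMPS, RBANS, WAIS-IV Digit Span, DKEFS subtests and BRIEF-A" plus mood, fatigue and agitation scales. It therefore includes AMPS and WAIS-IV Digit Span, but not MDS.

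Section 5.6 also plans t-tests of Active against Placebo on Maximum Cognitive Gain (MCG), for each outcome and session.

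**The concern.** A group-by-time parameter answers a question about gain when the series starts before treatment: the arms begin level, and divergence is the effect. The MDS series starts after treatment. Any difference already present at test 1 goes into the group term, and the interaction records only what happens to that difference afterwards. If the interaction is read as the answer to whether there was more gain, a real gain that holds looks like no effect, and a real gain that wears off looks like a disadvantage for Active.

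The trial's product is a set of effect estimates for a later crossover study. Aim 2 asks for both magnitude and duration, so a parameter that reflects change over the window but is used to settle magnitude could mislead that design.

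**Working it through.** **Inputs from the documents.** 24 Active and 24 Placebo; effect size 0.90; three post-intervention tests at 30-minute intervals; MDS at one session per Veteran. An even split between the two tests gives 24/2 = 12 Active and 12 Placebo per MDS series, before attrition.

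**Assumptions.** Two-sided 0.05 (section 5.6 states no alpha for the sample size); equal correlation ρ between a Veteran's tests, 0.6 to 0.8; the gain shapes below. The documents give neither correlations nor shapes.

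**The plan's own figure.** A two-sample t-test at effect size 0.90 and 80% power needs 21 per group (power 81%), 42 in all, and 42/(1 − 0.12) = 47.7, so 48. The plan's figure is reproduced. It concerns a level comparison. At 12 per arm, the same single-test comparison has 56% power.

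**Expected interaction, three post-tests.** With d_t the Active-minus-Placebo difference at test t and c = (−1, 0, 1), the slope per interval is Σc_t d_t / Σc_t² = (d₃ − d₁)/2.

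| Gain shape (SD) | Slope per interval |
|---|---|
| Sustained: 0.9, 0.9, 0.9 | (0.9 − 0.9)/2 = 0 |
| Half fade: 0.9, 0.675, 0.45 | (0.45 − 0.9)/2 = −0.225 |
| Full fade: 0.9, 0.45, 0 | (0 − 0.9)/2 = −0.45 |
| Building: 0, 0.45, 0.9 | (0.9 − 0)/2 = +0.45 |

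The zero for a sustained gain also holds if time is categorical. Fitting a random-intercept model to simulated data (300 runs per shape, ρ = 0.7) gave mean interactions of +0.001 (sustained), −0.448 (full fade) and +0.452 (building).

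**How often the interaction is significantly negative.** The standard error of the slope difference is √((1 − ρ)/12), with 22 degrees of freedom and critical t 2.07.

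| ρ | SE | Full fade: ratio, probability | Half fade: ratio, probability |
|---|---|---|---|
| 0.6 | 0.183 | −2.46, 65% | −1.23, 22% |
| 0.7 | 0.158 | −2.85, 78% | −1.42, 28% |
| 0.8 | 0.129 | −3.49, 91% | −1.74, 39% |

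For a sustained gain the test rejects 5% of the time, 2.5% in each direction. For the building gain, the full-fade probabilities apply with a positive sign.

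**Level contrast, sustained 0.9.** The mean of three tests has variance v = (1 + 2ρ)/3 and SE √((2/12)v), which is 0.350, 0.365 and 0.380. The ratios 0.9/SE are 2.57, 2.46 and 2.37, and power is 69%, 65% and 62%.

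**Adding a baseline covariate for MDS.** If WAIS-IV Digit Span at B0 correlates r with each MDS test, SE = √((2/12)(v − r²)(21/20)). The factor 21/20 allows for chance imbalance in the covariate, and there are 21 degrees of freedom. At r = 0.5, power is 84%, 79% and 74% for ρ = 0.6, 0.7 and 0.8. At r = 0.3 it is 73%, 68% and 64%.

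**AMPS with its pre-session value included.** Four points, treated as equally spaced, have c = (−1.5, −0.5, 0.5, 1.5) and Σc² = 5. A sustained gain (0, 0.9, 0.9, 0.9) gives 1.35/5 = 0.27 per interval, which is positive. A full fade (0, 0.9, 0.45, 0) gives (−0.45 + 0.225)/5 = −0.045, so a single linear slope shows a real early gain as about nothing.

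**The case against.** The strongest reply is that level is already tested. The MCG t-tests come first, the mixed model is introduced as an additional analysis, and the interaction's stated object is a differential trend. On that reading a negative interaction for a fading gain has the right sign for what it measures, and it informs duration, which Aim 2 wants. The fitted model would also contain a group term carrying the level difference.

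Part of this stands. Group-by-time is a legitimate description of time course, and a reader should not infer that Aim 2 has no level comparison at all, or that the model must report harm. What does not stand is the rescue of the sentence that asks the model about gain. No parameter other than the interaction is named for it, and the meaning of any group term depends on time coding the plan does not give. The MCG tests are no secure fallback: MCG is not defined, the reference to Table 1 leads to the eligibility criteria, and MDS has no baseline. If MCG were best minus first post-test, it would miss a sustained gain too.

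A second reply is that AMPS is measured before each session. That is correct, so a reader should not extend the zero result to AMPS. It applies there only if the pre-session value is left out. For MDS, the Aim 5 text speaks of scores before and after iTBS, but no study-day list schedules a pre-stimulation MDS.

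A third reply is that the time course is unknown. Section 5.5 says that "working memory shows the most consistent and largest effects (g=.938", but this is for healthy controls, with no time course, and calls the magnitude after one session in TBI and stroke unknown. A gain that builds would be detected. It is tempting to say that the analysis will miss the effect the plan expects; the documents do not fix the shape of that effect.

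**Conclusion.** The point holds for MDS. With only post-stimulation tests, the named parameter cannot establish whether Active iTBS, or Active iTBS + APT, gave more gain. The zero expectation for a sustained gain is algebra and needs no assumed correlation. The negative sign requires a fade within the three tests, and how often it reaches significance depends on the extent of the fade and the assumed correlations. The 65-91% range is for complete loss by the third test and should not be quoted without the 22-39% for a half fade.

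For AMPS the point is conditional: the plan should say whether the pre-session value enters the model, and even then one linear slope misreads a full fade.

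This is a should-fix. It is a secondary analysis in a pilot, and the documents attach no go/no-go decision to it.

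**What to change.** In section 5.6, Aim 2 (2i), define the mixed-model treatment parameter, for each outcome and session, as the Active-minus-Placebo difference averaged over the three post-intervention tests. Adjust it for diagnosis and for the B0 score already collected: AMPS for AMPS, and WAIS-IV Digit Span for MDS. Enter Digit Span as a covariate and do not subtract it, since it is a different form from MDS. Use B0 for both sessions, because B2 follows the first stimulation. State how time is coded. Keep group-by-time as a description of time course, and say that it will not be used to conclude whether a gain occurred.

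No visit, test or data item changes; the cost is SAP wording, best settled before analysis. The precision gained for MDS depends on how well Digit Span tracks it. At assumed correlations of 0.3 to 0.5, power for a sustained 0.9 SD gain is about 64-84%, against 62-69% unadjusted. Higher figures would need Digit Span to correlate with MDS about as strongly as MDS does with itself, which the documents do not show.

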## 5.6 Data Analysis

**Sample Size to Estimate Effect Sizes.** Our total sample size of 48 participants is based on 80% power to detect an Effect Size (ES) of .90. For 80% power, sample size per group to detect a small ES (0.35) is 130, for a medium ES (0.60) it is 42 and to detect a large ES (0.90) it is 21 per group. To estimate a large ES of 0.90, 42 subjects are required to achieve 80% power. Thus, we plan for 48 participants and 12% attrition.

Published methods  will be used to examine the merits of transdiagnostic sampling (Aim 1i). Specifically, we will use MLM to determine if neurologic diagnosis (stroke, TBI) moderates the effects of the Active intervention (Group 1: n = 24, Active iTBS and Active iTBS + APT; Group 2: n = 24, Placebo iTBS and Placebo iTBS + APT) on Maximum Cognitive Gain (MCG) as measured with the MDS and the AMPS.

For Aim 2, we will inform estimates of effect sizes by testing the idea (2i) that MDS gains and AMPS gains differ for Active iTBS and Active iTBS + APT. As specified in Table 1, we will examine if gains differ in magnitude by computing the MCGs for each outcome (MDS and AMPS) by each intervention. For each outcome, we will compare the Average Active iTBS MCG with the Average Placebo iTBS MCG and the Average Active iTBS + APT MCG with the

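### Hypothesis 2i (Active iTBS + APT versus Active iTBS) has no named test or interval in section 5.6, and the only parameter given after the additive-APT sentence compares two arms that both receive APT

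*Combined protocol and SAP*

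**What the plan says.** Section 3.0 (Aim 2, 2i) anticipates larger immediate AMPS gains after Active iTBS + APT than after Active iTBS alone, and says MCGs will be compared between those two conditions. Section 5.6 restates the aim as "testing the idea (2i) that MDS gains and AMPS gains differ for Active iTBS and Active iTBS + APT". It says the magnitude question will be answered by "computing the MCGs for each outcome (MDS and AMPS) by each intervention", and it refers to Table 1 for the specification.

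The analyses then named for Aim 2 are:

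- **MCG tests.** "For each outcome, we will compare the Average Active iTBS MCG with the Average Placebo iTBS MCG", and the same for Active iTBS + APT against Placebo iTBS + APT, by t-test or z-test.
- **Mixed model, iTBS session.** "Using MLM, we will also determine if Active iTBS is related to more MDS or more AMPS gains", followed by a group-by-time term for Active iTBS against Placebo iTBS.
- **Mixed model, iTBS + APT session.** "we will also use MLM to identify presence of an additive effect of APT by examining Active iTBS + APT trend lines". The next sentence says "the group (Active iTBS + APT or Placebo iTBS + APT) by time interaction parameter will be used" to look for a differential trend.
- **2ii.** "we will compare each PE measure for Active iTBS with Placebo iTBS and for Active iTBS + APT with Placebo iTBS + APT".
- **2iii.** One-tailed tests of peak gains after Placebo iTBS against Active iTBS.

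Under section 5.1, every Veteran receives APT with the assigned iTBS at the second intervention. Each Veteran is randomised to MDS or AMPS as the immediate-effects test at the first session and takes the other test at the second.

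**The concern.** The plan asks one question and specifies tests for another. Hypothesis 2i contrasts two active conditions that differ in APT. Each named comparison of interventions instead contrasts two conditions that differ in iTBS. The additive-effect sentence is the one place where section 5.6 turns to APT. It has no comparator, and the parameter that follows it holds APT constant.

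Two things are at stake. An analyst working from section 5.6 would have to choose the 2i contrast after seeing data, and no interval for it is pre-specified, although Aim 2 exists to inform effect estimates for a later cross-over study. The adjacent wording also invites a reader to take a session-2 iTBS effect as evidence that APT added something.

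**Working it through.** **1. Which comparisons could answer 2i?**

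| Analysis in 5.6 | Conditions compared | APT differs? |
|---|---|---|
| MCG tests | Active iTBS v Placebo iTBS; Active iTBS + APT v Placebo iTBS + APT | No |
| Group-by-time terms | the same two pairs | No |
| 2ii tests | the same two pairs | No |
| 2iii tests | Placebo iTBS v Active iTBS | No |
| Model question on more MDS or more AMPS gains | outcomes, not interventions | No |

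The Table 1 pointer does not fill the gap: Table 1 (section 5.4) is the eligibility table. Table 2 (section 5.5) lists instruments, not contrasts.

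**2. What does the session-2 term estimate?** Let a = iTBS effect, b = APT effect, c = iTBS-by-APT interaction, s = session order and practice, k = carry-over from the first active session. The letters may stand for mean gains or for slopes over time.

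- Placebo iTBS: 0
- Active iTBS: a
- Placebo iTBS + APT: b + s
- Active iTBS + APT: a + b + c + s + k

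The contrasts are:

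- Session 1, active minus placebo: a
- Session 2, active minus placebo: (a + b + c + s + k) - (b + s) = a + c + k
- 2i, Active iTBS + APT minus Active iTBS: b + c + s + k
- Placebo iTBS + APT minus Placebo iTBS: b + s

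The APT effect b cancels from both specified contrasts. Two illustrations with c = s = k = 0:

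- a = 0, b = 0.9: both specified contrasts are 0, while 2i is 0.9.
- a = 0.5, b = 0: the term placed after the additive-effect sentence is 0.5, while 2i is 0.

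Subtracting the two group-by-time terms does not recover 2i: (a + c + k) - a = c + k.

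**3. The plan's own sample size.** Two-sample t-test, effect size 0.90, 80% power, two-sided alpha 0.05 (assumed, since section 5.6 states no alpha for this calculation): 20.39, rounded up to 21 per group and 42 in total, as stated. With 12% attrition, 42/0.88 = 47.7, rounded up to 48, as stated.

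**4. Precision of the 2i contrast.** Each arm has 24 Veterans. With an even split, 12 active Veterans take a given immediate-effects test at session 1 and the other 12 take it at session 2. The contrast is therefore between Veterans, 12 v 12 per outcome. In SD units:

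- SE = sqrt(1/12 + 1/12) = 0.408
- Half-width = t(22) × SE = 2.074 × 0.408 = 0.85
- Noncentral-t power at 0.90 = 56%
- 80% power is reached near 1.20

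Attrition falls mainly on the second session. Section 5.7 keeps data collected before withdrawal and replaces Veterans who leave before any procedure past baseline. With 42 of 48 completing, 24 × 42/48 = 21 per arm, so 10 or 11 per session-2 cell against about 12 at session 1:

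- 12 v 11: SE 0.417, half-width 2.080 × 0.417 = 0.87, power at 0.90 = 54%
- 12 v 10: SE 0.428, half-width 2.086 × 0.428 = 0.89, power at 0.90 = 52%

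All power figures are before the false discovery rate control that section 5.6 applies to Aims 2 and 3.

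**The case against.** The best defence is that the contrast is declared. Section 3.0 commits to comparing MCGs between the two active conditions, section 5.6 repeats the idea, and both active means will be computed. In a pilot meant to inform estimation, an unnamed t-test is a small omission. Adding one also buys little, because APT always comes second and no analysis of these data can isolate it.

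Much of this stands, and it limits the point. A reader might infer that 2i has been abandoned. The documents do not support that: the intention is written twice, and what is missing is the test and its interval. A reader might also infer that the plan declares the session-2 group-by-time term to be the APT effect. It does not say so. It leaves the additive-effect sentence without a comparator and offers no other parameter.

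A third tempting reading is that the session-2 term can detect only differences that develop over the three post-stimulation tests. That is not established. The model's time points are undefined, and AMPS and WAIS-IV Digit Span (on which the MDS is based) are measured before stimulation at B0 and B2, so a pre-stimulation value could enter. It would not change the conclusion, since APT cancels either way.

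The defence does not remove the mismatch. A named active-versus-placebo term sits where the APT comparison should be, and inspecting trend lines yields no estimate against Active iTBS alone.

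**Conclusion.** The point holds as an analysis that does not match its hypothesis, and it should be fixed. Section 5.6 specifies no test, parameter or interval for 2i. The one parameter following the additive-effect sentence estimates the iTBS effect in the presence of APT, plus interaction and carry-over. The cancellation of a common APT effect follows from the design and needs no numerical assumption.

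The precision figures assume SD 1 in both cells, an even split of the immediate-effects tests and two-sided alpha 0.05. On that basis the direct contrast has a half-width of 0.85 SD and 56% power at 0.90, moving to 0.87-0.89 SD and 52-54% with session-2 dropout. The stated 21 per group does not apply to it. Naming the contrast makes 2i estimable as worded. It does not make APT separable from session order, practice or carry-over.

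**What to change.** 1. State that the session-2 group-by-time term is the iTBS effect in the presence of APT, together with any interaction and carry-over, and is not evidence of an additive APT effect.
2. Name Active iTBS + APT minus Active iTBS in MCG, with its 95% confidence interval, as the 2i contrast. Reconcile section 3.0, where 2i is directional and about AMPS, with section 5.6, where it is non-directional and covers MDS and AMPS.
3. Report Placebo iTBS + APT minus Placebo iTBS beside it. State that both differences mix APT with session order and practice, that the active one also contains iTBS carry-over and any iTBS-by-APT interaction, and that APT therefore cannot be isolated.
4. State that the contrast is between Veterans, about 12 v 12 per outcome, and give the expected precision.
5. Correct the Table 1 pointer so that it leads to a specification of the outcomes and contrasts.

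The cost is SAP wording and a few contrasts on data already planned, with no change to study conduct. The downside is a more modest 2i claim with wide intervals.
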